5.5.1.1 Pharmacodynamic, Pharmacokinetic, Pharmacogenomic, and Other Biomarker Analyses

Correlation between clinical response to treatment associated with a combination of lenvatinib and everolimus and blood or tumor biomarkers will be examined using descriptive statistics and graphic displays as appropriate. Details will be provided in a separate analysis plan.

Pharmacokinetic/pharmacodynamic exposure-safety relationships will be explored. Safety endpoints will be most frequent AEs of special interest and dose reductions. Exploratory/graphical analyses will be conducted for Pharmacokinetic/pharmacodynamic evaluations and may be followed by model-based analyses. A detailed analysis plan will be provided separately.

5.6 Safety Analyses

All safety analyses will be performed on the Safety Analysis Set. Safety data will be presented by planned dose level in Phase 1 and study cohort in Phase 2 and summarized on an “as treated” basis using descriptive statistics (e.g., n, mean, SD, median, Q1, Q3, minimum, and maximum values for continuous variables; n (%) for categorical variables). Safety variables include study drug exposure, treatment-emergent adverse events (TEAEs), laboratory tests, vital signs, 12-lead ECGs, cardiac function by echocardiography/MUGA scan, urine dipstick, and Lansky play scores or Karnofsky performance scores. Study Day 1 for all safety analyses is defined as the date of the first dose of study drug.

5.6.1 Extent of Exposure

5.6.1.1 Extent of Exposure of Study Drug

Parameters that represent the extent of exposure will be presented per dose level in Phase 1 and per study cohort in Phase 2, summarized separately for lenvatinib and everolimus. These include:

- No. of Cycles Received
- Cumulative No. of Cycles Received
- Duration of Treatment
- No. of Subject Weeks

Number of cycles received will be summarized by descriptive statistics and by categories. Duration of treatment (presented separately as days, weeks, and months) for oral drug Lenvatinib and everolimus will be summarized by descriptive statistics. Overall Duration of Treatment and No. of Subject Weeks will also be tabulated by dose level in Phase 1 and study cohort in Phase 2.

5.6.1.2 Study Drug Administration

Total cumulative dose per subject (mg) will be summarized separately for lenvatinib and everolimus by descriptive statistics. It is calculated as the sum of daily doses.

Dose intensity ($\text{mg}/\text{m}^2/\text{day}$) will be summarized separately for lenvatinib and everolimus by descriptive statistics. It is calculated as: Total cumulative dose per subject (mg) /BSA (m^2) / Duration of treatment (day).

The percentage of received dose relative to planned dose will be summarized separately for lenvatinib and everolimus by descriptive statistics. It is calculated as: dose intensity / planned dose level \times 100. Interpretation: 100 means received dose was the same as the planned, 90 means that the actual dose was 90% of the planned.

5.6.1.3 Study Drug Dose Modifications

Study drug dose modifications will be summarized separately for lenvatinib and everolimus, respectively.

Number of subjects with dose reductions or interruptions will be summarized by counts and percentage according to drug administration data, respectively. Cycle of first dose interruption/reduction will be summarized by descriptive statistics, respectively. Frequency of dose interruptions and dose reductions will also be summarized by appropriate categories (e.g., 1, 2, 3, ≥ 4).

The first dose reduction is defined as the first time the subject's daily dose level was reduced to a nonzero value from its maximum designated prescribed BSA-adjusted dose level and did not go back to the maximum designated BSA-adjusted dose level due to a reason other than BSA adjustment or drug administration error. For example, lenvatinib $11 \text{ mg}/\text{m}^2$ followed by $0 \text{ mg}/\text{m}^2$ followed by $8 \text{ mg}/\text{m}^2$. If there is only dose interruption with no reduction in dose, such an event will not be considered as a dose reduction. The second and subsequent dose reductions will be defined accordingly. In addition, time to first dose reduction among subjects with dose reduction will also be summarized.

Dose interruptions defined as below:

1. Only includes the scenario that before and after dose $0 \text{ mg}/\text{m}^2$ (interruption period), the

dose levels are the same. For example: 11 mg/m² followed by 0 mg/m² and followed by 11 mg/m²; 8 mg/m² followed by 0 mg/m² followed by 8 mg/m².

2. If dose level reduces from previous dose level after dose interruption period (dose 0 mg/m²), it should count as dose reduction and not dose interruption. For example: 11 mg/m² followed by 0 mg/m² followed by 8 mg/m², the period with 0 mg/m² should not count as dose interruption instead it should count as dose reduction.

3. If after dose level 0 mg/m², the subject discontinued from treatment permanently, it should count as treatment discontinuation instead of dose interruption.

Subject data listings will be provided for all dose administration records and for the variables calculated as above.

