9.4.1.1 Study Treatment Dose Reduction and Interruption Instructions

Dose reduction and interruptions for subjects who experience lenvatinib-everolimus combination therapy-related toxicity will be managed as described in [Table 5](#). Investigators will decide the probability of the event being related to protocol therapy as to whether dose modification of drug therapy is required.

Doses in the Dose Adjustment column are based on a presumed starting dose of 11 mg/m² lenvatinib and 3 mg/m² everolimus. Dose reductions will occur in succession based on the previous dose level. Each dose level reduction due to toxicity at a given BSA is

approximately 25% reduction from the previous dose. Once the study drug dose has been reduced, it may not be increased at a later date, unless the dose was mistakenly decreased; in this situation, the sponsor's approval is required to increase the dose.

Asymptomatic laboratory abnormalities, including Grade ≥ 3 abnormalities (eg, elevations of amylase and lipase) that are not considered clinically relevant by the investigator, should be managed per institutional guidelines; continuation of treatment should be discussed with the sponsor.

Table 5 Dose Modification Guidelines for Lenvatinib-Everolimus Combination Treatment-Related Toxicity

Treatment-Related Toxicity ^{a,b}	Management	Dose Adjustment
Grade 1 or Tolerable Grade 2		
	Continue treatment	No change
Intolerable Grade 2^{c, d, e} or Grade 3^f		
First occurrence	Interrupt lenvatinib and everolimus until resolved to Grade 0-1 or tolerable Grade 2	Reduce lenvatinib dose to 8 mg/m ² (or approximately 25% reduction of the starting dose) orally once a day (one-level reduction) and resume everolimus at the same dose as prior to dose interruption
Second occurrence (same toxicity or new toxicity)	Interrupt lenvatinib and everolimus until resolved to Grade 0-1 or tolerable Grade 2	Reduce lenvatinib dose to 6 mg/m ² (or approximately 25% reduction from the previous dose level) once a day (one-level reduction). Dose reduction of everolimus to 3 mg/m ² every other day may be considered for Grade 3 toxicity ^e

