Third occurrence (same toxicity or new toxicity)	Interrupt lenvatinib and everolimus until resolved to Grade 0-1 or tolerable Grade 2	Reduce lenvatinib dose to 4.5 mg/m ² (or approximately 25% reduction from the previous dose level) orally once a day (1-level reduction). Dose reduction of everolimus for Grade 3 toxicity: i) if 3 mg/m ² daily everolimus at event onset, reduce to 3 mg/m ² every other day or

		ii) if 3 mg/m ² every other day everolimus at event onset, discontinue
Fourth occurrence (same toxicity or new toxicity)	Interrupt lenvatinib and everolimus	Discuss with sponsor
Grade 4^g: Discontinue Study Treatment		

Note: For grading see Common Terminology Criteria for Adverse Events (CTCAE) v4.03. Collect all CTC grades of adverse events, decreasing and increasing grade.
 
a: An interruption of study treatment for more than 28 days will require sponsor’s approval before treatment can be resumed.
 
b: Initiate optimal medical management for nausea, vomiting, hypothyroidism and/or diarrhea prior to any study treatment interruption or dose reduction.
 
c: Applicable only to Grade 2 toxicities judged by the subject and/or physician to be intolerable.
 
d: Obese subjects with weight loss do not need to return to the baseline weight or 10% of baseline weight (ie, Grade 1 weight loss). These subjects will restart the study drug(s) at a lower dose once their weight remains stable for at least 1 week and they reached the normal body mass index (BMI; if the weight loss occurred but it is still above normal BMI, they can restart the study treatment at a lower dose once the weight has been stable for at least 1 week). Normal BMI should be used as the new baseline for further dose reductions. See BMI charts for boys (Appendix 9) and girls (Appendix 10).
 
e: For Grade 2 toxicity, resume everolimus at the same dose as prior to dose interruption. For Grade 3 toxicity, investigator will decide the probability of the event being related to one or both drugs as to whether dose modification of one or both drugs is required.
 
f: For asymptomatic laboratory abnormalities, such as Grade ≥3 elevations of amylase and lipase that are not considered clinically relevant by the investigator, continuation of treatment should be discussed with the sponsor.
 
g: Excluding laboratory abnormalities judged to be non-life-threatening, in which case manage as Grade 3.
		

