9.7.1.7 Pharmacokinetic, Pharmacodynamic, Pharmacogenomic, and Other Biomarker Analyses

9.7.1.7.1 PHARMACOKINETIC ANALYSIS

Lenvatinib and everolimus concentration versus time data will be tabulated and summarized and graphically presented.

Plasma concentrations of lenvatinib from the intense sampling in Phase 1 will be used to determine the following PK parameters: area under the plasma concentration time course profile (AUC), maximum observed concentration (C_{max}), and time from dosing to the maximum observed concentration (T_{max}). Other PK parameters may be determined as data permit.

For both lenvatinib and everolimus, data from Phase 1 and 2 of the study will be pooled with available data from other studies and subjected to population PK analysis. For each drug, the PK model will be parameterized in terms of clearance and volume of distribution.

Details of the population PK analysis will be provided in a separate analysis plan.

9.7.1.7.2 PHARMACODYNAMIC, PHARMACOKINETIC/PHARMACODYNAMIC, PHARMACOGENOMIC, AND OTHER BIOMARKER ANALYSES

Correlation between clinical response to treatment associated with a combination of lenvatinib and everolimus and blood or tumor biomarkers will be examined using descriptive statistics and graphic displays as appropriate. Details will be provided in a separate analysis plan.

Pharmacokinetic/PD exposure-safety relationships will be explored. Safety endpoints will be most frequent AEs of special interest and dose reductions. Exploratory/graphical analyses will be conducted for PK/PD evaluations, and may be followed by model-based analyses. A detailed analysis plan will be provided separately.

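### Read literally, SAP 5.6.1.3 does not count Table 5's every-other-day everolimus step as a dose reduction for a subject on 3 mg/m²

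*SAP*

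**What the plan says.** **Protocol 9.4.1.1, Table 5.** The table's scope is set by the sentence beginning "Doses in the Dose Adjustment column are based on a presumed starting dose"; for everolimus that dose is 3 mg/m². For intolerable Grade 2 or Grade 3 toxicity, the everolimus actions are:

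- First occurrence: "resume everolimus at the same dose as prior to dose interruption".
- Second occurrence: 3 mg/m² "every other day may be considered for Grade 3 toxicity".
- Third occurrence, Grade 3: a subject on daily dosing goes to every other day. For a subject already on the alternate-day schedule the entry is "every other day everolimus at event onset, discontinue".

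There is no step to a lower mg/m² per administration.

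**SAP 5.6.1.3.** Modifications are summarised separately for each drug from drug administration data, under one set of definitions. A first reduction occurs when the "daily dose level was reduced to a nonzero value from its maximum designated prescribed BSA-adjusted dose level" and does not return to that maximum. An interruption is a 0 mg/m² period with the same dose level before and after it. The section then states: "If there is only dose interruption with no reduction in dose, such an event will not be considered as a dose reduction". All its worked examples use lenvatinib levels (11, 8 and 0 mg/m²). The SAP nowhere mentions every-other-day dosing.

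**The concern.** The definitions fit lenvatinib, whose Table 5 steps are falls in mg/m² (11 to 8 to 6 to 4.5). They do not fit a step taken by frequency. On every other day at 3 mg/m², each dosing day is back at the maximum level, so the test for a reduction fails both on size and on the condition of not returning to the maximum. The pattern 3, 0, 3 also matches the definition of an interruption.

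At stake are the everolimus summaries that describe tolerability, which is a Phase 2 secondary objective: the number of subjects reduced, the cycle of first reduction, the time to first reduction, and possibly the frequency of interruptions. With at most 20 evaluable subjects per cohort, one misclassified subject moves a rate by 1/20 = 5 percentage points.

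**Working it through.** The plan states no figure to reproduce, so the check applies the SAP rules to sequences of daily dose levels.

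**Rules used (SAP 5.6.1.3).** A move to a lower nonzero level is a reduction. A zero run with the same level on both sides is an interruption. A zero run followed by a lower level is a reduction only. A zero run followed by permanent stop is a discontinuation.

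**Check on the SAP's own cases.** 11-0-8 gives 1 reduction. 11-0-11 and 8-0-8 give 1 interruption each. A zero followed by permanent stop gives discontinuation. All agree with the SAP.

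**Applied to Table 5:** 28 days at 3 mg/m² daily, then 28 days of 3-0-3-0, with dosing continuing.

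| How the switch is held in the data | Reductions | Interruptions |
|---|---|---|
| Off-days entered as 0 mg/m² | 0 | 14 |
| Same, after a 7-day toxicity hold (assumed length) | 0 | 15 |
| One record, dose 3 with a frequency field, no zero rows | 0 | 0 |
| Averaged to 1.5 mg/m²/day (not specified in the SAP) | 1 | 0 |

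- Off-days per cycle: 28 / 2 = 14.
- Time to the ≥4 category: off-days fall on days 2, 4, 6 and 8. The fourth starts on day 8 and ends when dosing resumes on day 9.
- Average dose on the schedule: 14 × 3 / 28 = 1.5 mg/m²/day, and 1.5 / 3 = 50% of planned.
- Dose intensity under SAP 5.6.1.2 is taken over the whole treatment duration, so the fall is diluted by time on daily dosing. In this example it is (28 × 3 + 14 × 3) / 56 = 126 / 56 = 2.25 mg/m²/day, or 75% of planned.

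**Dose Level 3.** From 4.5 mg/m², a literal move to Table 5's 3 mg/m² every other day, after the same 7-day hold, gives 1 reduction, plus 14 interruptions if zeros are recorded. The missed reduction therefore applies to subjects on 3 mg/m².

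**The case against.** The strongest reply is that SAP 5.6.1.3 leaves the case open. It tests a daily dose level against a prescribed level, and SAP 5.6.1.2 works in mg/m²/day, so a programmer could treat 3 mg/m² every other day as 1.5 mg/m²/day and count one reduction. Programming rules sit in separate documents. That is possible, but the SAP does not specify averaging, and its rule for a zero period with an unchanged level points the other way. A derivation document should implement the definition, not supply it.

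Other parts of the reply stand and limit the point:

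- A reader might infer that interruption counts are bound to be inflated. That needs off-days stored as 0 mg/m², and the documents do not show the eCRF layout.
- A reader might infer that the everolimus reduction rate will be 0% whatever happens. That fails for a 4.5 mg/m² start. The protocol also allows everolimus changes outside Table 5 (9.4.1.8, 9.4.1.9, 9.4.7.1).
- A reader might infer that the table of TEAEs leading to dose reduction (SAP 5.6.2) must disagree. It might. No split by drug is stated there, and Table 5 reduces lenvatinib for the same event, so the event may appear in that table for that reason.
- A reader might infer harm to the exposure-safety analysis, because Protocol 9.7.1.7.2 says "Safety endpoints will be most frequent AEs of special interest and dose reductions". That analysis has its own separate plan, and nothing shows that it takes over the everolimus definition in 5.6.1.3.
- The step arises only at a second or later occurrence and only for Grade 3 toxicity, and it is optional at the second. Dose intensity, percentage of planned dose and the listings of dosing records would still carry the information.

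**Conclusion.** The point holds in a limited form. Followed as written, SAP 5.6.1.3 does not count the Table 5 everolimus step as a reduction for a subject on 3 mg/m². This is so under both unaveraged data layouts. The reduction count, cycle of first reduction and time to first reduction for everolimus would miss it.

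The second effect is conditional: about 14 interruptions per 28-day cycle if off-days are stored as 0 mg/m², and none if the switch is one record with a frequency field. One prescribed change can thus be reported in different ways depending on data entry, which a pre-specified definition should prevent.

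The impact is confined to descriptive tolerability tables. DLT assessment, the Week 16 response rate and the futility decisions do not use these rules. This should be corrected, but it does not threaten the trial's main conclusions.

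**What to change.** Add to SAP 5.6.1.3:

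1. A prescribed change of everolimus from daily to every other day is one dose reduction, dated at the start of the new schedule. Identify it from the average prescribed daily dose over the dosing interval (3 to 1.5 mg/m²/day) or from the recorded frequency.
2. Scheduled off-days of that regimen are not interruptions. Only unplanned zero-dose periods beyond the schedule count.
3. Add an everolimus worked example beside the lenvatinib ones.

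Under this rule the sequence of 28 days daily then 28 days every other day gives 1 reduction and 0 interruptions.

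The cost is a few lines of SAP text and matching programming. It needs the prescribed schedule to be identifiable in the dosing data, which the sponsor should confirm against the eCRF. The dosing rule itself does not change, and no protocol amendment is needed.

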5.6.1.4 Dose Limiting Toxicity

DLTs will be recorded during Cycle 1 (Day 1 to Day 28) for subjects in Phase 1. The BSA, DLT (Yes/No/Not Evaluable) and reason(s) for each subject will be listed, as well as the date, and dosage of drug when the DLT occurred.

5.6.2 Adverse Events

The adverse event (AE) verbatim descriptions (investigator terms from the eCRF) will be classified into standardized medical terminology using MedDRA version 21.1 or higher. Adverse events will be coded to the MedDRA lower level term (LLT) closest to the verbatim term. The linked MedDRA preferred term (PT) and primary system organ class (SOC) are also captured in the database.

A treatment-emergent adverse event (TEAE) is defined as an AE that had an onset date on or after the first dose of study drug up to 28 days following the last dose of study drug, or a worsening in severity from Baseline (pretreatment). In addition, if an AE reemerges during treatment, having been present at pretreatment (Baseline) but stopped before treatment, it is also counted as TEAE. The Common Terminology Criteria for Adverse Events (CTCAE) version 4.03 will be used to assess the severity of AEs.

Only those AEs that are treatment emergent will be included in summary tables. All AEs, treatment emergent or otherwise, will be presented in subject data listings. TEAEs will be summarized by dose level in Phase 1 and by cohort in Phase 2.

The incidence of TEAEs will be reported as the number (percentage) of subjects with TEAEs by SOC and PT. A Subject will be counted only once within an SOC and PT, even if the subject experiences more than 1 TEAE within a specific SOC and PT. The number (percentage) of subjects with TEAEs will also be summarized by highest CTCAE grade. The number (percentage) of subjects with treatment-related TEAEs will also be summarized by SOC and PT. Treatment-related TEAEs include those events considered by the investigator

to be related to study treatment or missing causality.

In summary, the following TEAE tables will be provided if appropriate:

- Overview of TEAEs
- TEAEs by SOC and PT
- TEAEs in decreasing frequency of PT
- TEAEs by SOC, PT, and CTCAE grade
- TEAEs with CTCAE Grades ≥ 3 by decreasing frequency of PT
- Overview of treatment-related TEAEs
- Treatment-related TEAEs by SOC and PT
- Treatment-related TEAEs by SOC, PT, and Worst CTCAE grade
- Treatment-related TEAEs by decreasing frequency of PT with CTCAE Grades ≥ 3

The number (percentage) of subjects with Grade 5 (fatal) TEAEs will be summarized by MedDRA SOC and PT and a subject data listing of all deaths (whether or not treatment emergent) will be provided. All deaths reported will also be summarized in a table.

The number (percentage) of subjects with treatment-emergent SAEs will be summarized by MedDRA SOC and PT. A subject data listing of all SAEs will be provided. The number (percentage) of subjects with TEAEs leading to discontinuation, dose reduction, or dose interruption of study drug will also be summarized by MedDRA SOC and PT. A subject data listing of all AEs leading to discontinuation, dose modification (reduction or interruption) of study drug will be provided.

In summary, the following tables will be provided if appropriate:

- All deaths in the safety analysis set
- Grade 5 (fatal) TEAEs by decreasing frequency of PT
- Grade 5 (fatal) TEAEs by SOC and PT
- Treatment-emergent SAEs by SOC and PT
- Treatment-emergent SAEs by SOC, PT and Worst CTCAE Grade
- Treatment-related treatment-emergent SAEs by SOC and PT
- Treatment-related treatment-emergent SAEs by SOC, PT and Worst CTCAE Grade
- Treatment-emergent SAEs by decreasing frequency of PT
- Nonfatal treatment-emergent SAEs by SOC and PT
- TEAEs leading to study drug discontinuation by SOC and PT
- TEAEs leading to study drug dose reduction and/or dose interruption by SOC and PT

- TEAEs leading to study drug dose reduction by SOC and PT

Clinically significant treatment-emergent AEs (CSAEs) for lenvatinib include: arterial TE (thromboembolic) events, bone and teeth abnormalities, cardiac dysfunction, hypothyroidism, GI (gastrointestinal) perforation, fistula formation, hemorrhage, hypertension, hypocalcemia, hepatotoxicity, palmar plantar erythrodysesthesia syndrome (PPE), proteinuria, QT prolongation, renal events, posterior reversible encephalopathy syndrome (PRES), and pneumothorax.

Adverse events of special interest (AEOSI) for everolimus include: Angioedema, Dyslipidemia, Pneumonitis, and Stomatitis.

The number and percentage of each category of treatment-emergent CSAEs for lenvatinib and AEOSI for everolimus will be summarized by overall, CTCAE grade and by dose level for Phase 1 and by cohort for Phase 2. Time to first onset of CSAEs for lenvatinib and AEOSI for everolimus will also be summarized.

The following tables will be provided only for CSAEs for lenvatinib and AEOSI for everolimus.

- Summary of CSAEs for lenvatinib and AEOSI for everolimus by category and PT
- Summary of serious CSAEs for lenvatinib and AEOSI for everolimus by category and PT
- Overview of CSAEs for lenvatinib and AEOSI for everolimus by category
- Incidence and Time to First Onset of CSAEs for lenvatinib and AEOSI for everolimus

The following tables will be provided only for subjects in Phase 1.

- TEAEs in Cycle 1 in decreasing frequency of PT
- TEAEs in Cycle 1 by SOC and PT
- TEAEs in Cycle 1 with CTCAE Grades ≥ 3 by decreasing frequency of PT

The following subject AE listings (treatment-emergent or otherwise) will be provided:

- All AEs
- All deaths for all enrolled subjects
- All SAEs
- All AEs leading to study drug discontinuation
- All AEs leading to dose reduction and / or dose interruption
- Subjects with Febrile Neutropenia
- All CSAEs

The following subject listings will be provided only for subjects in Phase 1.

- DLTs in Cycle 1
- TEAEs in Cycle 1

